##### *Study population for descriptive analysis (secondary objective #2)*

- Pregnant women received prenatal care at KPSC
- Vaccinated with Boostrix before the 27th week of gestation and were not vaccinated with any other Tdap vaccine at any other time during the pregnancy
- Membership at the index (vaccination) date

##### *Subgroups for endpoint-specific analysis*

For some maternal and infant AEs (endpoints), additional restriction criteria will be applied. We will exclude individuals who do not meet the restriction criteria, but not the matched pair. Analysis will be conducted on a subgroup of the population:

- Small for gestational age (SGA): Infants 1) live born, 2) singleton, and 3) born in KPSC hospitals. Rationale: The evaluation of SGA is limited to singleton births because the reference values for SGA definition are established based on singleton births. The birth weight of infants born outside KPSC hospitals is not captured in claims, and such infants are therefore excluded for this endpoint.

- Preterm delivery: Pregnant women 1) with live birth and 2) with index (vaccination) date prior to 37 weeks gestation. Rationale: Pregnant women with an index (vaccination) date on or after 37th week of gestation are not at risk of preterm delivery, and are therefore excluded for this endpoint.
- Preterm pre-labor rupture of membranes (PPROM): Pregnant women with index (vaccination) date prior to 37 weeks gestation. Rationale: Pregnant women with an index (vaccination) date on or after 37th week of gestation are not at risk of PPROM, and are therefore excluded for this endpoint.
- Transfusion during delivery hospitalization: Pregnant women with delivery hospitalization. Rationale: Transfusion can be captured by procedure codes during the delivery hospitalization.
- Stillbirth/fetal death: Pregnant women with pregnancy outcome. Rationale: Pregnant women with unknown pregnancy outcome are considered as missing data, and are therefore excluded for this endpoint.
- Neonatal death (within 28 days of birth) and congenital anomalies at birth and through 6 months of age: Infants 1) live born and 2) born in KPSC hospitals. Rationale: Infants born outside KPSC hospitals may not be captured and may not be able to be linked back to their pregnant mothers, and are therefore excluded for this endpoint.

Analysis for preeclampsia and/or eclampsia, intra-uterine infections, poor fetal growth, placental abruption, and maternal death will be conducted on all pregnant women eligible for the main analysis and descriptive analysis.

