### **3.2 Study population, exposures, outcomes and covariates**

#### **3.2.1 Study populations/subgroups**

##### *Study population for main analysis (primary objective and secondary objective #1)*

- Pregnant women received prenatal care at KPSC
- Exposed cohort: vaccinated with Boostrix on the 1st day of the 27th week of pregnancy or later during the pregnancy and were not vaccinated with any other Tdap vaccine at any other time during the pregnancy or
- Unexposed cohort: pregnant at least one day during the approximate estimated period between 1/1/2012-12/31/2013 and did not receive any Tdap vaccine during the pregnancy
- Continuous membership (allowing up to a 31-day gap) between the 1st day of the 27th week of pregnancy and the index (vaccination) date

The unexposed cohort will be 1:1 matched to the exposed cohort on age at pregnancy start ( $\pm 1$  year), race/ethnicity (White, Black, Hispanic, Asian, and Other), and multiple gestation (yes/no). Every unexposed woman will be assigned an index date that is determined by the number of days from pregnancy start to the Boostrix vaccination date of her matched exposed woman. The same number of days calculated in the exposed woman will be added to the pregnancy start of the unexposed woman to determine her index date.

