Health care utilization will be defined as any hospitalization or emergency department (ED) visit, and number of outpatient visits (0-4, 5-12,  $\geq 13$ ) from pregnancy start to index date.

Receipt of other vaccines during pregnancy will be defined as any receipt of other vaccines from pregnancy start to index date.

The covariates included in adjusted analyses will be determined by scientific relevance, association with exposure and outcome, and data availability. Specifically, we will select covariates by following these steps:

1. The distribution of covariates will be reviewed. Those covariates in the same category with rare events will likely be combined as a single covariate. For example, we might consider grouping all chronic conditions into a single covariate.
2. The data availability will be checked. If a covariate contains a large proportion that is missing, and the proportion missing is differential by exposure, then the covariate may not be included.
3. Association of covariates with exposure will be assessed. We will use standardized difference to assess the balance of covariates between exposed and unexposed cohorts. Unlike p-values, for which magnitude is highly related to sample size, standardized difference is a unified approach to quantifying the magnitude of difference between groups regardless of sample size, where an absolute value less than 0.1 is considered a negligible difference (3). We will use a SAS macro %stddiff developed by PPD and PPD (4) to calculate the standardized differences for continuous and categorical variables. Potential confounders will be determined by absolute standardized difference (ASD)  $>0.1$ .
4. Association of potential confounders (identified from step 3) with each primary endpoint will be further assessed using a change-in-estimate approach (5). Diabetes, pre-existing hypertension (except for the analysis of the preeclampsia and/or eclampsia endpoint), Medicaid insurance, and health care utilization, which are considered as the most representative prognosis factors, will be kept in the adjusted model regardless of their association with exposure and primary endpoints. For a specific endpoint, the exposure coefficient estimate from a model adjusted for the 4 above covariates will be compared with the estimate from a model adjusted for one more covariate at a time. Covariates which result in a 10% change in the exposure coefficient estimate will be selected for final adjusted analysis.

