5. All potential confounders (identified from step 3) will be included in the analyses of secondary endpoints. If the outcome is rare and the adjusted model cannot converge, problematic covariates will be removed from the model. If total counts from the two groups (i.e., sum of events in the exposed and unexposed cohorts) is less than 5, then no adjusted analysis will be performed.

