Preeclampsia and/or eclampsia	All pregnant women eligible for main analysis	Adjusted Poisson regression model accounting for follow up time, with robust variance estimate
Intra-uterine infections	All pregnant women eligible for main analysis	Adjusted Poisson regression model accounting for follow up time, with robust variance estimate
SGA	KPSC live born infant, singleton only*	Adjusted Poisson regression model, with robust variance estimate
Preterm delivery	Pregnant women with live birth, with index date prior to 37 weeks gestation	Adjusted Poisson regression model, with robust variance estimate

\*There are no well accepted SGA metrics for infants born to pregnant women with multiple gestation

Limiting analyses of endpoints to subgroups (e.g., KPSC live born infant) may cause matches to be broken, although we expect the proportions of non-live births and non-KPSC births to be small.

The matching variables will be included in the adjusted models of analyses of SGA and preterm delivery. Age at pregnancy start will be adjusted as a categorical variable (<24/25-34/≥35 years).

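### Matching variables are put back into the SGA and preterm models when pairs break, but not into four secondary models where pairs can break in the same way

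*SAP*

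**What the plan says.** All references are to SAP version 2.0.

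- **Matching (3.2.1).** "The unexposed cohort will be 1:1 matched to the exposed cohort on age at pregnancy start" within one year, and also on race/ethnicity in five groups and on multiple gestation as yes/no.
- **Index day (3.2.1).** Pair members share a gestational index day by construction: an identical "number of days calculated in the exposed woman will be added to the pregnancy start of the unexposed woman to determine her index date".
- **Exclusions (3.2.1, endpoint-specific subgroups).** "We will exclude individuals who do not meet the restriction criteria, but not the matched pair".
- **Remedy (4.2).** The SAP notes that subgroup limits can break matches and gives KPSC live-born infants as its example. It expects non-live and non-KPSC births to be few. It then states: "The matching variables will be included in the adjusted models of analyses of SGA and preterm delivery".
- **Secondary models (3.2.4, step 5).** "All potential confounders (identified from step 3) will be included in the analyses of secondary endpoints". Step 3 sets the screen: "Potential confounders will be determined by absolute standardized difference (ASD"), with a cut-off of 0.1, assessed between the exposed and unexposed cohorts.
- **Section 4.3**, on secondary endpoints, does not mention the matching variables.

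**The concern.** The SAP's own example of a population in which matches may break, KPSC live-born infants, is the analysis population for neonatal death and congenital anomalies. The remedy reaches SGA but not those two endpoints, nor transfusion or stillbirth.

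The cohorts come from different eras, about 2012–2013 and 2018–2019. An unknown outcome, an unrecorded delivery hospitalization or a birth outside KPSC could therefore be more common in one of them, and could vary with age, race/ethnicity or multiple gestation. Protocol 4.1 chose matching variables on the ground that such factors can put a pregnancy at risk. An uncorrected imbalance could push a relative risk either way. A secondary signal is declared when the lower 95% limit of the adjusted relative risk exceeds 1, without multiplicity adjustment. A bias could thus add to false signals or help to hide a real one.

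**Working it through.** The plan's only power figure (95.7% at 1% incidence, true relative risk 1.25, 15,000 per cohort, one-sided 0.625%) reproduces at 95.71% with the score test for a ratio. This point does not depend on it.

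**Step 1: which restricted secondary analyses can break pairs?**

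| Endpoint | Restriction | Level | Matching variables required in model? |
|---|---|---|---|
| PPROM | "Pregnant women with index (vaccination) date prior to 37 weeks gestation" | Pair (index day shared) | No, and not needed |
| Transfusion | Delivery hospitalization | Individual | No |
| Stillbirth/fetal death | Pregnancy outcome known | Individual | No |
| Neonatal death | Live born in a KPSC hospital | Individual | No |
| Congenital anomalies | Live born in a KPSC hospital | Individual | No |

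Four of the five can break pairs. With exclusion proportions e1 and e0 in the two cohorts, and losses independent within pairs, the share of pairs broken is e1(1−e0) + e0(1−e1). This is 2.0% at 1%/1%, 9.5% at 5%/5% and 14% at 5%/10%.

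**Step 2: could the screen pick the matching variables up?** Step 3 compares the cohorts, where 1:1 matching should hold these variables well below 0.1. No check within an endpoint subgroup is written.

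**Step 3: how large could the bias be?** The documents give no exclusion rates, so every loss pattern and outcome risk below is an assumption.

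*Twin infants, neonatal death.* Assume 2% twin pregnancies, a 5-fold risk in twin infants, no loss of twins in the exposed cohort and a proportion l lost in the unexposed. Relative rate = (0.98 + 5×0.04(1−l)) / (0.98 + 0.04(1−l)).
- l = 0: 1.1569
- l = 0.2: 1.1265, spurious ratio 1.1569/1.1265 = 1.027
- l = 0.4: 1.0956, spurious ratio 1.056

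*Race group, stillbirth.* Take a group of 8.3% (protocol Table 1), a 2-fold risk, and loss in one cohort only. Relative rate = (0.917 + 2×0.083(1−l)) / (0.917 + 0.083(1−l)).
- l = 0: 1.0830
- l = 0.1: 1.0753, spurious ratio 1.007
- l = 0.2: 1.0675, spurious ratio 1.0145

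*A factor at 16%* (near the 15.8% aged 36–45 in protocol Table 2). With pE and pU its prevalence after exclusions and r its outcome relative risk, the bias is (1 + pE(r−1)) / (1 + pU(r−1)). Here k is how many times likelier exclusion is among women with the factor.

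| Exclusions, exposed / unexposed | k, exposed / unexposed | pE, pU | Standardized difference | Bias, r = 2 | Bias, r = 5 |
|---|---|---|---|---|---|
| 1% / 1% | 2 / 1 | 0.1588, 0.1600 | 0.003 | 0.999 | 0.997 |
| 5% / 10% | 2 / 2 | 0.1539, 0.1471 | 0.019 | 1.006 | 1.017 |
| 10% / 20% | 2 / 2 | 0.1471, 0.1310 | 0.047 | 1.014 | 1.042 |
| 2% / 20% | 1 / 3 | 0.1600, 0.1091 | 0.150 | 1.046 | 1.142 |

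The last row is a stress case, far from the few exclusions that the SAP expects.

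**Step 4: would a screen at 0.1 inside the subgroup catch these?** The standardized differences are 0.041 and 0.088 in the twin scenarios, and 0.028 and 0.059 in the race scenarios. All are below 0.1. Of the 16% rows, only the stress case would be caught.

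**Step 5: effect on false signals.** Assume 50 events per cohort. The standard error of the log relative risk is √(2/50) = 0.2, and the chance of a false elevated signal is 1 − Φ(1.96 − ln(bias)/0.2). Against a nominal 2.5%, it is 2.7–3.0% in the race scenarios and 3.4–4.6% in the twin scenarios. With 200 events per cohort (standard error 0.1) and 40% twin loss it is 7.8%.

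**The case against.** The strongest case against acting is that the effect is close to nothing. Intact pairs still balance the matching variables. A broken pair biases the comparison only if exclusion is related to those variables, and differently or at different rates in the two cohorts. SAP 4.2 expects few non-live and non-KPSC births, and SAP 5.1 expects very little missing data after chart review. The transfusion restriction, "Transfusion during delivery hospitalization: Pregnant women with delivery hospitalization", does not require a KPSC hospital. The power section already allows for a design bias of 1.25, well above 1–6%. A signal would also lead, under SAP 4.5, to incidence stratified by age and other risk factors.

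Most of this stands and limits the point to a small one. Two parts do not remove it. Few exclusions overall do not exclude concentrated loss: the twin scenarios lose only 0.04×0.2/1.02 = 0.8% and 0.04×0.4/1.02 = 1.6% of unexposed infants. And SAP 4.5 acts only after a signal, so it cannot reveal one that bias has hidden.

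Three stronger readings are tempting, and the documents do not support them.
- *The four analyses lose control of the matching variables.* They do not; balance is only no longer guaranteed.
- *The matching variables can never enter the secondary models.* SAP Table 2 lists them as covariates, and SAP 3.2.4 and 4.1 also name scientific relevance as a criterion. The N/A entries in Shell 2 are in the p-value column and say nothing about standardized differences. The numbered steps make selection unlikely, not impossible.
- *Infants are unbalanced even before exclusions, because matching was by pregnancy.* Mothers are matched on multiple gestation, so what remains is mainly twins against higher-order births, and the yes/no covariate would not correct that.

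**Conclusion.** The inconsistency is on the page: one exclusion rule and the same kind of broken pairs, but a remedy written for two endpoints and not for four others. The selection steps give the matching variables no assured route into those four models.

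The consequence is probably small: about 1–6% on the relative risk under one-sided or strongly differential loss, and near zero if exclusions are few and similar. That range rests on assumed loss patterns and risk ratios; only the 8.3% and 15.8% shares come from the documents. For the rarest outcomes, random error will exceed the bias. The four endpoints are hypothesis-generating, and no primary conclusion is affected. This is a low-cost consistency correction.

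**What to change.** Add to SAP 4.3: *for transfusion, stillbirth/fetal death, neonatal death and congenital anomalies, age at pregnancy start, race/ethnicity and multiple gestation will be included in the adjusted model where event counts allow, subject to step 5 of Section 3.2.4.* Step 5 already drops problematic covariates on non-convergence and omits adjusted analysis below five events in total.

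Also report the standardized difference of each matching variable within each endpoint subgroup. Use it for description and not as the gate for adjustment, because a 0.1 gate would miss the twin and race scenarios above.

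If the age bands in SAP 4.2 (<24/25-34/≥35) are reused, correct them first: age 24 falls in no band.

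The cost is one sentence and variables already collected. The downside is up to seven extra parameters (race/ethnicity 4, age 2, multiple gestation 1). With an assumed 2% of events in multiple gestations, the chance that none of 20 events falls there is 0.98^20 = 0.67, and for 50 events it is 0.98^50 = 0.36. Terms may therefore have to be dropped for neonatal death and the anomaly subtypes. Fixing the order of removal in advance would keep that from being driven by the data.

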### 3.2.2 Exposures

Boostrix vaccination will be received as part of routine clinical care. Vaccine exposure will be identified retrospectively from the electronic health records, including vaccine, manufacturer, and lot number entered at the time of vaccination.

### 3.2.3 Primary and secondary endpoints

Primary endpoints (Table 1) were selected based on their medical relevance, also considering the background incidence or prevalence of these endpoints.

Secondary endpoints (Table 1) were differentiated from primary endpoints to allow evaluation of the safety of maternal vaccination with sufficient statistical power on the primary endpoints, and to allow for hypothesis generation/signal detection on secondary endpoints.

Table 1. List of primary and secondary endpoints

Primary endpoints	Preeclampsia and/or eclampsia
	Intra-uterine infections such as chorioamnionitis and endometritis
	Small for gestational age (SGA)
	Preterm delivery
Secondary endpoints	Transfusion during delivery hospitalization
	Poor fetal growth

Stillbirth/fetal death with or without congenital anomalies
Neonatal death (within 28 days of birth)
Maternal death (while pregnant or within 42 days of end of pregnancy)
Placental abruption
Preterm pre-labor rupture of membranes (PPROM)
Congenital anomalies at birth and through 6 months of age
Congenital anomalies of nervous system
Congenital anomalies of eye
Congenital anomalies of ear, face, or neck
Congenital anomalies of cardiovascular system
Congenital anomalies of respiratory system
Clefts
Congenital anomalies of upper gastrointestinal system
Congenital anomalies of lower gastrointestinal system
Congenital anomalies of genital organs
Congenital anomalies of renal system
Congenital anomalies of musculoskeletal system
Congenital anomalies of limb
Congenital anomalies of integument
Other and unspecified congenital anomalies
Spontaneous abortion with or without congenital anomalies (only for women exposed to Boostrix before the 27 th week of gestation)
Therapeutic abortion with or without congenital anomalies (only for women exposed to Boostrix before the 27 th week of gestation)

The algorithms for identification of primary and secondary endpoints are described in the DMP. Except SGA, preterm delivery, and transfusion during delivery hospitalization, AEs identified through the algorithms will be chart reviewed to confirm the diagnosis and the onset (when applicable). Analyses of endpoints will be based on confirmed cases. For AEs with a chart-reviewed onset date, the event start date will be the onset date; for AEs without a chart-reviewed onset date (unknown or inapplicable), the event start date will be the earliest confirmed diagnosis date. To be a confirmed case, the event start date needs to be after the index date. Some AEs might be diagnosed during the delivery hospitalization, and have an event start date after the delivery date. For pre-eclampsia and/or eclampsia, intra-uterine infections, and poor fetal growth, the event date needs to be on or before the delivery date. For placental abruption and PPROM, if the event start date is after the delivery date, the delivery date will be used as the event start date.

SGA will be defined based on reference values derived by Talge et al. with a cut-off of <10th percentile (1). Talge et al used 2009-2010 US natality data and corrected for likely errors in gestational age dating to yield an up-to-date birth weight for gestational age reference. The

evaluation of SGA is limited to singleton births because the reference values for SGA definition are established based on singleton births.

Stillbirth/fetal death has a number of different and legally mandated definitions (2). This study will use ACOG's definition which defines stillbirth/fetal deaths at 20 completed weeks gestation or greater (if the gestational age is known). Maternal death will include all non-accidental deaths while pregnant or within 42 days of end of pregnancy. Neonatal death will include deaths within 28 days of birth among KPSC live born infants.

For a multiple gestation pregnancy, the pregnancy outcome will be recorded for each fetus, while the endpoint will be defined by the worst scenario. For examples, the woman will be considered to have a pre-term delivery, if any fetus was delivered pre-term after the index date. The woman will also be considered to have spontaneous abortion, therapeutic abortion, or stillbirth/fetal death if any fetus experienced these pregnancy outcomes after the index date.

For a multiple gestation pregnancy with multiple live births, only the infant(s) with infant AEs (neonatal death and congenital anomalies) will be chart reviewed. The endpoint will be defined at the infant level.

Additional birth outcomes will be captured among KPSC born infants for descriptive purposes, but will not be considered as AEs: birth length, head circumference, and Apgar scores.

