Safety events following Tdap immunization during pregnancy have been increasingly examined in recent years. A placebo-controlled clinical trial of Adacel administered to pregnant women (2008-2012) found no Tdap-associated serious adverse events (12). During a time when Tdap was not routinely recommended for pregnant women, spontaneous abortions were the most frequent pregnancy-specific adverse events (16.7%) identified through the Vaccine Adverse Event Reporting System (VAERS), a national database used for monitoring the safety of vaccines in the population (13). However, the number of pregnant women who received the vaccine was small (n=132) and likely a selective group since the vaccine was not in routine use. A small study observing a limited number of maternal and infant outcomes (chorioamnionitis, postpartum endometritis, premature rupture of membranes, 5-minute Apgar score, birth defects) also found no Tdap-associated adverse events (14). However, the authors found that Tdap was associated with women having decreased odds of cesarean delivery. In a study of 2010-

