2. OBJECTIVE

2.1. Primary objective

To rule out a two-fold increase (non-inferiority testing) in the incidence of each of the following maternal and infant adverse events:

- Preeclampsia and/or eclampsia
- Intra-uterine infections such as chorioamnionitis and endometritis
- Small for gestational age (SGA)
- Preterm delivery

among women who were vaccinated with Boostrix on or after the 1st day of the 27th week of gestation as compared to the incidence in a historical cohort of pregnant women (approximately January 1, 2012 to December 31, 2013) who were unvaccinated with any Tdap vaccine throughout their pregnancy.

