### **3. STUDY DESIGN**

#### **3.1 Overview of study design**

This is an observational retrospective matched cohort study. The study will be conducted among pregnant women who are members of KPSC.

The exposed cohort (from the 27th week of gestation) will consist of pregnant women who received the Tdap vaccine (Boostrix) on or after the 1st day of the 27th week of pregnancy during the vaccination period at ob-gyn clinics of seven selected medical centers. Approximately 15,000 women vaccinated with Boostrix will be included in this study over approximately a one-year period from January 2018 to January 2019.

The unexposed cohort will consist of women, pregnant sometime during the approximate estimated period from 1/1/2012 to 12/31/2013 who never received Tdap vaccine during pregnancy. The unexposed cohort of pregnant women will be matched 1:1 to the exposed cohort of pregnant women for comparisons of maternal and infant AEs between the two cohorts.

Subject-level data will be collected for pregnant women and their infants through the EHR. For each individual pregnant woman, analytical follow up will begin on the date they receive the Boostrix vaccine, or the index date for the unvaccinated cohort, and will end on the date of

disenrollment or the end of pregnancy, whichever came first. For the maternal death endpoint, pregnant women will be followed for 42 days after the end of pregnancy. Infants born in KPSC hospitals will be followed for 6 months.

In addition, women vaccinated with Boostrix before the 27th week of gestation, with membership at the date of vaccination, and who were not vaccinated with any other Tdap vaccine at any other time during the pregnancy will be included for a descriptive analysis (single arm).

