##### 4.2 Analyses of primary endpoints

We will calculate crude incidence and 95% CI for each primary endpoint for the exposed and unexposed cohorts. Unadjusted and adjusted RR with two-sided 98.75% CI will be estimated comparing the exposed cohort to the unexposed cohort, accounting for multiple comparisons.

Analysis of primary endpoints will be used to evaluate the safety of Boostrix vaccination and concluded to be non-inferior if the upper limit of the 98.75% CI for the adjusted relative risk is below 2.

Analyses of preeclampsia and/or eclampsia and intra-uterine infection will be performed on all pregnant women eligible for main analysis. For events identified any time after the index date (e.g., preeclampsia and/or eclampsia and intra-uterine infection), the incidence will consist of the total number of women with the condition in the numerator and the total person time in the denominator. The person-year for a pregnant woman will be the time from the index date to the date of each adverse event, end of the pregnancy, or disenrollment, whichever comes first. The unadjusted and adjusted relative risk with 98.75% CI will be estimated by Poisson regression models accounting for the follow-up time without and with adjustment for potential confounders. If the outcome is common (i.e., incidence > 2%), a Poisson regression model with a robust error variance will be used to estimate the relative risk (6). The robust Poisson regression will be performed using the SAS Proc GENMOD procedure with the REPEATED statement subject= Patient\_ID.

Analysis of SGA will be performed on live singleton infants born in KPSC hospitals, while analysis of preterm delivery will be performed on pregnant women with live births, and with an index date prior to 37 weeks gestation. For events identified at delivery (e.g., SGA and preterm delivery), the incidence will consist of the total number of women or infants with the condition in the numerator and the number of women or infants for whom the condition can be assessed in the denominator. The unadjusted and adjusted relative risk with 98.75% CI will be estimated by Poisson regression models with robust error variances without and with adjustment for potential confounders. The planned methods of analysis by primary endpoint are outlined in Table 4. See Appendix A, Table Shell 4 for details.

Table 4. Analytic population and statistical methods by primary endpoint

Primary endpoints	Analytic population	Statistical Methods

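### The primary endpoint names endometritis with no time limit, but only infections dated on or before delivery count, and the dating rule also drops some confirmed chorioamnionitis

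*SAP*

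**What the plan says.** Protocol section 2.1 lists as a primary endpoint "Intra-uterine infections such as chorioamnionitis and endometritis". Protocol Table 6, SAP section 2.1 and SAP Table 1 use the same name. None of them gives a time window.

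SAP section 3.2.3 sets the counting rules:

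- Where chart review yields no onset date, the diagnosis date stands in: "for AEs without a chart-reviewed onset date (unknown or inapplicable), the event start date will be the earliest confirmed diagnosis date".
- A cut-off at delivery applies to three endpoints: "For pre-eclampsia and/or eclampsia, intra-uterine infections, and poor fetal growth, the event date needs to be on or before the delivery date".
- Two other endpoints are treated differently: "For placental abruption and PPROM, if the event start date is after the delivery date, the delivery date will be used" as the start date.

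The same section recognises that some events diagnosed in the delivery hospitalization will carry a start date later than delivery.

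Person-time for intra-uterine infection (SAP section 4.2) is "the time from the index date to the date of each adverse event, end of the pregnancy, or disenrollment, whichever comes first". Among the maternal endpoints, only death is followed longer. SAP section 3.1 says "For the maternal death endpoint, pregnant women will be followed for 42 days after the end of pregnancy", and SAP Table 1 puts that window in the endpoint's name: "Maternal death (while pregnant or within 42 days of end of pregnancy").

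**The concern.** There are two separate problems.

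**Scope.** The name covers endometritis without limit, but the count stops at delivery. Protocol section 1.1, describing an earlier Tdap study, lists "maternal and infant outcomes (chorioamnionitis, postpartum endometritis, premature rupture of membranes" among its outcomes, so the protocol itself uses the term for a condition that can arise after birth. If the endpoint passes, the conclusion would be worded for all intra-uterine infection and would cover events that were never counted. Footnote a of Table Shell 4 gives only the analysis population, so the report would not correct that reading.

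**Undated chorioamnionitis.** Whether a confirmed case counts can depend on whether someone charted an onset. Charting may differ between the 2012–2013 and 2018–2019 cohorts, and unequal loss biases the relative risk. SAP section 4.5 provides confirmation rates by cohort only when a signal is investigated. If the endpoint passes, nobody sees how many confirmed cases the date rule removed.

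This endpoint deserves care because Protocol section 1.1 reports a raised risk of chorioamnionitis after Tdap in more than one earlier study.

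**Working it through.** **Step 1. What the rules do to each type of case**

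| Confirmed case | Date assigned | Result |
|---|---|---|
| Chorioamnionitis, onset charted on or before delivery | Onset | Counted if after the index date |
| Chorioamnionitis, no charted onset, first confirmed diagnosis after delivery | Diagnosis | Dropped |
| Abruption or PPROM, no charted onset, first confirmed diagnosis after delivery | Moved to delivery | Counted if after the index date |
| Endometritis, onset after the delivery date | Onset | Dropped |

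Row 2 assumes that *event date* in the cut-off sentence means the same as *event start date* in the sentences around it. That is the natural reading.

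**Step 2. The plan's own power figure**

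Inputs from SAP section 3.3: 15,000 per cohort, 1% incidence in the unexposed, true relative risk 1.25, margin 2, one-sided alpha 2.5%/4 = 0.625%. A Miettinen–Nurminen score calculation gives 95.7%, the stated value. Simulation gives 96.0% and a Wald test on the log relative risk gives 96.5%. The plan's power is not in dispute.

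**Step 3. Endometritis named but not measured**

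The documents give no rate for endometritis after delivery. Assuming 0.5% to 2%: 15,000 × 0.005 = 75 and 15,000 × 0.02 = 300 cases per cohort.

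**Step 4. Effect of losing undated chorioamnionitis**

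Let c be the full incidence in the unexposed, and let LE and LU be the shares of cases lost in the exposed and unexposed cohorts. These shares are assumptions. Then

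- p1 = 1.25 × c × (1 − LE) and p0 = c × (1 − LU)
- observed RR = 1.25 × (1 − LE)/(1 − LU)
- SE(log RR) = √[(1 − p1)/(n·p1) + (1 − p0)/(n·p0)], with n = 15,000
- 98.75% limits = RR × exp(±2.498 × SE)

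Two values of c are used: 5.5%, the chorioamnionitis rate among unvaccinated women in an earlier study cited in Protocol section 1.1, and 1%, the planning floor.

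Example with no loss, c = 5.5%: p1 = 0.06875, p0 = 0.055, SE = 0.0453, upper limit = 1.25 × exp(2.498 × 0.0453) = 1.400.

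| LE | LU | RR factor | RR | 98.75% CI, c = 5.5% | 98.75% CI, c = 1% | Wald power, c = 1% |
|---|---|---|---|---|---|---|
| 0 | 0 | 1.000 | 1.250 | 1.116–1.400 | 0.952–1.641 | 0.965 |
| 5% | 10% | 1.056 | 1.319 | 1.173–1.485 | 0.994–1.752 | 0.878 |
| 10% | 5% | 0.947 | 1.184 | 1.053–1.332 | 0.893–1.571 | 0.984 |
| 0 | 10% | 1.111 | 1.389 | 1.236–1.561 | 1.049–1.839 | 0.773 |
| 10% | 0 | 0.900 | 1.125 | 1.002–1.263 | 0.851–1.487 | 0.996 |

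Equal loss leaves the RR at 1.250. At c = 5.5%, power exceeds 0.999 in every row. For the upper limit to reach 2 with loss in the unexposed cohort only, that loss would have to be 29.1% at c = 5.5% or 16.7% at c = 1%.

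**The case against.** The strongest reply on scope is that the limit is neither hidden nor in conflict with the analysis. It is pre-specified, and it agrees with follow-up (Protocol section 3.3, SAP section 3.1) and with person-time (Protocol section 6.2.2, SAP section 4.2). The protocol's analysis section speaks of incidence during pregnancy. Endpoints may carry a window in the list only when they run past the default end of follow-up, and the objective leaves out other operational limits too, such as the restriction of SGA to singletons. All of that is true, and it means the cut-off itself can stay. The mismatch between the name and the count remains: endometritis is named, part of it can begin after the cut-off, and neither the endpoint list nor the results footnote says so.

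On undated cases, the reply is that chart review is meant to find the onset, that the identification algorithms sit in the data management plan and abstraction guidance in a separate manual, neither available here, and that nothing shows how many such cases exist. The number is indeed unknown. But the dating rule is in the SAP, which points to no exception elsewhere. Moving every late-dated infection to delivery would misclassify true post-delivery endometritis. That is a sound warning, and it is why the change below is limited to chorioamnionitis.

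Finally, the numbers show little threat to the margin result. That stands as well.

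**Conclusion.** The concern holds in both parts and should be fixed before analysis. The conclusion as planned would be wider than its data, because endometritis with onset after the delivery date cannot count. The dating rule for undated chorioamnionitis is wrong as written: it discards confirmed cases that the SAP would keep for abruption and PPROM.

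The effect is on what may be claimed and on possible unseen bias, not on the expected outcome of the test. Assumed unequal losses of up to 10% multiply the relative risk by 0.90 to 1.11. At a true relative risk of 1.25, every upper limit stays below 2. Power is a concern only if the incidence is near 1%. These figures rest on assumed losses, on unadjusted Wald intervals, and on 15,000 women per cohort. The true number of affected cases cannot be derived from the documents.

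**What to change.** 1. In SAP section 3.2.3, use the delivery date as the event start date for confirmed chorioamnionitis with no charted onset and a first confirmed diagnosis after delivery. Report the number of such cases in each cohort whether or not the endpoint signals.
2. In the SAP endpoint definition, the Table Shell 4 footnote and the study conclusion, describe the endpoint as intra-uterine infection with onset on or before delivery, and state that endometritis with later onset is not assessed. Carry the same wording into the protocol objective at the next amendment.

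The cost is low. The first change is one programming rule and one count by cohort from cases already chart reviewed. If the data management plan keeps cases first coded after discharge out of chart review, that should be stated alongside the count. The second change is wording only and alters no estimate. Neither should need a new data extraction.
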